4.4.3. Vaccine Viremia

The level of vaccine viremia and shedding will be assessed for all subjects by RT-qPCR in blood, urine, and saliva. For RT-qPCR results reported as < LLOQ, the result will be assigned a value of LLOQ/2 at such visit for computations. For RT-qPCR results reported as < LOD, the result will be assigned a value of 1 genome copies/mL for computations.

Vaccine viremia duration is defined as the time from first administration of study vaccine to vaccine viremia clearance detected by RT-qPCR. Subjects without vaccine viremia clearance will be censored at the last evaluable assessment.

The distribution for vaccine viremia duration by treatment group will be estimated by Kaplan-Meier methodology and the 25th percentile, median, 75th percentile, number and percentage of events and censored observations, and appropriate 95% CIs will be presented. If the 95% CIs of

three PHV01 groups overlap then the analysis will be repeated comparing the combined PHV01 group with the placebo group. The corresponding Kaplan-Meier curves will also be generated.

The proportion of subjects with vaccine viremia in blood, urine, and saliva, as well as the geometric mean of vaccine viremia level and the geometric mean of peak level, will be presented on Day 1 (at 0 and 6 hours), 2, 4, 8, 15, and 29 by specimen type, dose level and the combined PHV01 group.

Reverse cumulative distribution curves of rVSV RNA copies by specimen type will be generated by treatment group on Day 1 (at 0 and 6 hours), 2, 4, 8, 15, and 29, respectively, where the x-axis will be the observed log-10 transformed titers and the y-axis will be the percentage of subjects having a log-10 transformed titer greater than or equal to each of the observed log-10 transformed titers on the x-axis.

Line plots will present number of rVSV RNA copies by specimen type at each visit by treatment group.

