1.1.3.2. Immunogenicity and Efficacy

Two studies in guinea pigs given graded doses of an uncloned, development lot, the cloned master viral seed, or final drug substance showed development of vaccinemia, vaccine-specific antibodies and protection against lethal challenge using a guinea pig adapted MARV. In animals inoculated with $2x10^4$ or $2x10^6$ pfu of the final drug substance, 83% and 100% survived challenge, respectively. See the Investigator's Brochure for details.

Two studies in cynomolgus macaques were conducted with a development lot and with the toxicology lot 155941 of PHV01 at 6.7×10^7 and 1.6×10^7 pfu, respectively. All animals developed vaccinemia peaking on day 1 and clearing by day 4-7 indicating active replication of the vaccine virus. IgG GP-binding and neutralizing antibodies were elicited by day 14, and all animals survived lethal challenge on day 42 with MARV (Angola), whereas control animals inoculated with 0.9% saline succumbed within 8 days. Please see the IB for details of these studies.

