- Incidence of AESIs up to Day 181, including pneumonitis, acute respiratory distress syndrome, multiorgan failure, a hemorrhagic diathesis, certain neurologic events (encephalitis, myelitis, aseptic meningitis, optic neuritis, transverse myelitis, generalized convulsions, Guillain-Barré Syndrome, acute disseminated encephalomyelitis), thrombocytopenia, anaphylaxis, and vasculitides.

Secondary safety endpoints include the following:

• PHV01 in blood on Days 1 (at 0 and 6 hours), 2, 4, 8, 15, and 29, as detected by quantitative reverse transcription polymerase chain reaction (RT-qPCR)

- o Proportion of subjects with viremia detected by RT-qPCR
- Median duration of viremia, determined by RT-qPCR
- o Geometric mean level of viremia, geometric mean peak level of viremia, and area under the curve (AUC)
- PHV01 in urine, saliva, biopsy, joint fluid, vesicle fluid, or swab of other suspect lesions on Days 1 (at 0 and 6 hours), 2, 4, 8, 15, and 29, as detected by RT-qPCR
 - o Proportion of subjects with PHV01 detected by RT-qPCR
 - o Median duration of PHV01, determined by RT-qPCR
 - Geometric mean copy number of PHV01, geometric mean peak copy of PHV01, and AUC

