3.2. General Methods

All data listings that contain or imply an evaluation date will contain a relative study day (Rel Day). Pre-treatment and on-treatment study days are numbered relative to the day of the first dose of study medication which is designated as Day 1. The preceding day is Day -1, the day before that is Day -2, etc. Post-treatment study days are numbered relative to the first dose and are designated as Day 1, Day 2, etc. for table and listing display. Data for time interval analysis and graphing will be displayed as days since dosing where Hour 6 timepoint on Day 1 is converted to 0.25 days.

All outputs will be incorporated into Microsoft Word or Excel files, or Adobe Acrobat PDF files, sorted and labeled according to the International Conference on Harmonisation (ICH) recommendations, and formatted to the appropriate page size(s).

Tabulations will be produced for appropriate demographic, baseline, immunogenicity, and safety parameters. For categorical variables, summary tabulations of the number and percentage of subjects within each category (with a category for missing data) of the parameter will be presented. For continuous immunogenicity variables, the number of subjects, geometric mean, median, geometric standard deviation (SD), minimum, and maximum values will be presented.

Other continuous variables (e.g., BMI) will be summarized by the number of subjects, mean, median, SD, minimum, and maximum values. Summarizations will be tabulated by treatment group.

Formal statistical hypothesis testing will be performed on the primary and secondary immunogenicity endpoints with all tests conducted at the 2-sided, 0.05 level of significance. Summary statistics will be presented, as well as CIs on selected parameters, as described in the sections below.

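### Viremia duration is analysed by Kaplan-Meier as if clearance were observed exactly, although it is only bracketed by two samples; on the natural reading the median is overstated, by roughly 1 to 3 days if clearance falls in the Day 4 to Day 8 gap

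*SAP*

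**What the plan says.** SAP 1.2.5.1 lists as a secondary safety endpoint "Median duration of viremia, determined by RT-qPCR", based on "PHV01 in blood on Days 1 (at 0 and 6 hours), 2, 4, 8, 15, and 29". SAP 4.4.3 gives the definition: "Vaccine viremia duration is defined as the time from first administration of study vaccine to vaccine viremia clearance detected by RT-qPCR". The only censoring rule is "Subjects without vaccine viremia clearance will be censored at the last evaluable assessment". The estimator is stated as "The distribution for vaccine viremia duration by treatment group will be estimated by Kaplan-Meier methodology", with quartiles and 95% confidence intervals. Protocol 7.5.2 also names Kaplan-Meier for duration.

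The intervals have a planned use. Under SAP 4.4.3, if those of the three dose groups overlap, the analysis is repeated with the doses pooled against placebo. No formal test of duration between doses is planned.

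Neither document mentions interval censoring or says which date clearance takes when it falls between two samples. Protocol 3.1.3 defines vaccinemia as a result at or above the LLOQ. SAP 4.4.3 handles results below the LLOQ and below the LOD differently for computation, but does not say which of them counts as clearance, or whether one negative sample is enough. It gives no rule for subjects who are never viremic.

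**The concern.** Kaplan-Meier with right censoring takes each event time as known. Here it is never known: a subject positive on Day 4 and negative on Day 8 cleared at some point in between. Entering the Day 8 date as the event time shifts the estimate upward and produces a confidence interval that reflects sampling variation between subjects but not the unobserved gap.

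The median is a named endpoint of a first-in-human study of a replicating vaccine, and the RT-qPCR viremia results are due to feed the interim analysis that guides dose selection (SAP 3.12; Protocol 7.2 makes their inclusion depend on availability). A report of 7 days could be carried forward as a finding when the data support only a time after day 3 and up to day 7. The same intervals also decide whether the doses are pooled.

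**Working it through.** The plan states no expected duration, precision or power for this endpoint, so there is no figure to reproduce.

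**Inputs from the documents**
- Sampling days 1 (0 h and 6 h), 2, 4, 8, 15 and 29 (SAP 1.2.5.1). On the SAP 3.2 scale of days since dosing, where "Hour 6 timepoint on Day 1 is converted to 0.25 days", these are 0, 0.25, 1, 3, 7, 14 and 28, with gaps of 0.25, 0.75, 2, 4, 7 and 14 days.
- Windows of ±1 day at both Day 4 and Day 8 (Protocol Table 2), so that gap can run from (8 − 1) − (4 + 1) = 2 days to (8 + 1) − (4 − 1) = 6 days.
- Macaques: "All animals developed vaccinemia peaking on day 1 and clearing by day 4-7" (Protocol 1.1.3.2).
- Ten subjects per dose (Protocol 7.1).

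**Assumptions.** No human data exist (Protocol 1.2). True durations are taken as lognormal with log-SD 0.25, 0.4 or 0.6. All subjects are viremic, and clearance is dated at the first negative sample and is permanent.

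**Step 1: large-sample shift.** With true time T, the recorded time is R = the smallest sampling time at or after T. Rounding up preserves order, so the reported median is the first sampling time at or after the true median m, and the shift is R(m) − m.

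| True median m (days) | Reported | Shift |
|---|---|---|
| 2 | 3 | 3 − 2 = 1 |
| 4 | 7 | 7 − 4 = 3 |
| 5 | 7 | 7 − 5 = 2 |
| 6 | 7 | 7 − 6 = 1 |

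Inside this gap the shift stays below 7 − 3 = 4 days. If clearance is uniform over 4 to 7 days, the median of 5.5 is reported as 7 (+1.5). If the macaque range counts dosing as Day 1, it becomes 3 to 6 days since dosing, and 4.5 is reported as 7 (+2.5).

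**Step 2: groups of 10, log-SD 0.4.** The median is the first time at which the curve is at or below 50%. On nominal days, true medians of 4, 5 and 6 give mean reported medians of about 6.7, 7.0 and 7.7, and 7 is the most frequent value in all three. The mean overstatement per subject is about 2.3, 2.6 and 3.0 days. With whole-day visit windows, the mean reported medians are 6.4, 7.1 and 8.1.

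**Step 3: two doses of 10.** The log-rank test is used only as a gauge, since the SAP does not plan it.

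| True medians | Log-SD | Same reported median, nominal days | Log-rank power, exact times → visit-dated |
|---|---|---|---|
| 4 vs 6 (same gap) | 0.25 | 97% | 90% → 45% |
| 4 vs 6 | 0.4 | 84% | 55% → 43% |
| 4 vs 6 | 0.6 | 69% | 31% → 26% |
| 2 vs 5 (different gaps) | 0.25 | 0% | 100% → 100% |
| 2 vs 5 | 0.4 | 0.4% | 99% → 98% |
| 2 vs 5 | 0.6 | 4% | 87% → 84% |

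With windows and log-SD 0.4, 4 vs 6 gives identical medians in 20% of runs and the right order in 76%. Software that averages two times when the curve sits exactly at 50% will show fewer ties.

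**Step 4: what is not biased.** The proportion still viremic at a sampling day is the same either way. For m = 4 and log-SD 0.4, it is 76.4% at day 3 and 8.2% at day 7 with exact or visit-dated times.

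**Step 5: the alternative.** With complete, on-schedule samples, the Turnbull estimate equals Kaplan-Meier at each sampling day. The difference is that the median is reported as (3, 7] rather than 7.

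**The case against.** The best defence has four parts.

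- **Disclosed convention.** The SAP says clearance is the one detected by RT-qPCR, so the figure can be read as an upper bound, and for a safety endpoint rounding up is the cautious direction. This stands in part, but nothing in the planned output labels the median as an upper bound, and the confidence interval is still too narrow for what was observed.
- **Unbiased results are already planned.** SAP 4.4.3 reports the proportion viremic at each sampling day by dose, with reverse cumulative curves and line plots. This stands and limits the harm. It does not correct the named median.
- **The direction depends on unstated rules.** Never-viremic subjects entered at 0 or 0.25 days would shorten a group's median. This stands, so the overstatement is claimed only among viremic subjects with clearance dated at the first negative sample.
- **Small descriptive study.** There are 36 subjects, and SAP 3.1 says the size was not chosen for formal testing. This is a reason not to add a dose test. It is no reason to report an interval as a point.

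A reader might infer that doses cannot be told apart. The documents and the check do not support that. Doses that clear in different gaps separate with little loss, and visit windows restore most of the ordering within a gap. A reader might also infer that clearance is expected across the 7- and 14-day gaps. The only documented range points to the Day 4 to Day 8 gap. It comes from macaques given 1.6×10⁷ and 6.7×10⁷ pfu, above the highest human dose of 1×10⁷ pfu, so carrying it over to humans is itself an assumption.

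**Conclusion.** The point holds in a limited form. SAP 4.4.3 treats an interval-censored time as exactly observed. Among viremic subjects, with clearance dated at the first negative sample and human clearance resembling the macaque range, the median is overstated by roughly 1 to 3 days (less than 4 on nominal visit days), and its confidence interval omits the unobserved gap.

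Doses clearing within the same gap will often report the same median when visits fall on their nominal days. That is a property of the schedule and of 10 subjects per dose, not of Kaplan-Meier, and no estimator recovers it. The sizes rest on assumed lognormal durations. The structural fault does not depend on that assumption.

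**What to change.** In SAP 4.4.3:

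1. Analyse duration as interval-censored on (last positive sample, first negative sample], using actual sampling times as SAP 4.4.4 already does for AUC. Use the Turnbull estimator, for example SAS PROC ICLIFETEST, and report the median as an interval such as (3, 7] days since dosing.
2. Define clearance: below LLOQ or below LOD, and a single or a sustained negative result.
3. State how never-viremic subjects, including placebo recipients, enter the analysis.
4. Base the overlap step that leads to pooling on the interval-censored results.

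No dose-comparison test needs to be added.

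The cost is SAP wording and a little more programming, with no new samples. Protocol 7.5.2 names Kaplan-Meier, so the departure should be recorded as Protocol 7.7 and SAP 6 provide. The downside is a median reported as a wider interval, and differences inside one gap remain unresolved.

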4.4. Safety Analyses

Safety analyses will be conducted using the ASaT population.

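### Viremia clearance is undefined and never-viremic subjects have no rule, so the median duration and the placebo Kaplan-Meier comparison cannot be interpreted

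*SAP*

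**What the plan says.** SAP 1.2.5.1 lists as a secondary safety endpoint "Median duration of viremia, determined by RT-qPCR", with sampling for "PHV01 in blood on Days 1 (at 0 and 6 hours), 2, 4, 8, 15, and 29". The same section asks for a median duration of PHV01 in urine, saliva and lesion samples.

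SAP 4.4.3 gives the derivation: "Vaccine viremia duration is defined as the time from first administration of study vaccine to vaccine viremia clearance detected by RT-qPCR". The censoring rule follows: "Subjects without vaccine viremia clearance will be censored at the last evaluable assessment". On the method it says: "The distribution for vaccine viremia duration by treatment group will be estimated by Kaplan-Meier methodology". If the confidence intervals of the three dose groups overlap, "the analysis will be repeated comparing the combined PHV01 group with the placebo group".

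The analysis set comes from SAP 4.4: "Safety analyses will be conducted using the ASaT population". Under SAP 2.1 that is everyone who received any part of an injection and has on-study safety data. Nothing in 4.4.3 limits the duration analysis to subjects who ever had a positive sample, and the planned repeat against placebo shows that no such limit is intended.

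Protocol 3.1.3 defines vaccinemia as a PCR result at or above the LLOQ. SAP 4.4.3 sets numerical values for results below the LLOQ and below the LOD, but does not say which of these counts as clearance. Protocol 7.5.2 promises a median duration and a Kaplan-Meier plot, and gives no rule for never-viremic subjects.

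**The concern.** A time-to-clearance analysis needs subjects who have something to clear, and a definition of when it has gone. Here the population includes people who may never be positive: the 6 placebo recipients, and possibly some vaccinees at the lower doses. The plan does not say whether such a person has an event or is censored, or at what time. The programmer must choose, and the two obvious choices send these subjects to opposite ends of the time axis.

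At stake are a named secondary safety endpoint, its comparison with placebo and, if the rule is carried over, the matching durations in urine and saliva. A median that moves with the number of never-viremic subjects mixes how often viremia occurs with how long it lasts.

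**Working it through.** The documents give no figure for viremia duration, so there is none to reproduce. The check runs the Kaplan-Meier estimate on the planned sampling grid under each reading of clearance.

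**Inputs from the documents**
- Group sizes: 10 per dose, 30 vaccinees, 6 placebo (SAP 3.1).
- Post-dose sampling times in days since dosing: 0.25, 1, 3, 7, 14, 28 (SAP 1.2.5.1, with the 6-hour sample set to 0.25 day in SAP 3.2).

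**Assumptions**
- All placebo samples are negative.
- Every subject is followed to the Day 29 visit.
- Viremic vaccinees are positive from 6 hours and all clear, half on the Day 4 sample (3 days) and half on the Day 8 sample (7 days). The extra one goes to 3 days when the number is odd.
- The number viremic per dose group, v, is not given in the documents, so the full range of 0 to 10 is shown.

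**Formula.** S(t) is the product, over event times up to t, of (1 − events / number at risk). The median is the first time at which S(t) ≤ 0.5.

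**Reading A: clearance requires an earlier positive.** Never-viremic subjects have no event and are censored at 28 days.
- Placebo: 0 events, 6 censored, S = 1.0 throughout, no median.
- v = 4: S(3) = 1 − 2/10 = 0.8; S(7) = 0.8 × (1 − 2/8) = 0.6. The curve stays there, so there is no median.
- v = 8: S(3) = 1 − 4/10 = 0.6; S(7) = 0.6 × (1 − 4/6) = 0.2. The median is 7 days.
- v = 10: S(3) = 1 − 5/10 = 0.5. The median is 3 days.

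When all viremic subjects clear, S ends at (10 − v)/10. With v ≤ 4 it never falls below 0.6, so the loss of the median does not depend on the assumed clearance times.

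**Reading B: clearance is the first negative post-dose sample.** Never-viremic subjects have an event at 0.25 day.
- Placebo: 6 events in 6 at 0.25 day, median 0.25 day.
- v = 5: S(0.25) = 1 − 5/10 = 0.5. The median is 0.25 day.
- v = 6: S(0.25) = 1 − 4/10 = 0.6; S(3) = 0.6 × (1 − 3/6) = 0.3. The median is 3 days.

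Reading B also misclassifies some viremic subjects. A vaccinee who is negative at 6 hours and positive on Day 2 is counted as cleared at 0.25 day, before viremia has been seen. Protocol 1.1.3.2 reports vaccinemia peaking on day 1 in macaques, so this sequence is plausible.

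**Median duration (days) in a dose group of 10**

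| Viremic, of 10 | Reading A | Reading B | Ever-positive only | Never-positive set to 0 |
|---|---|---|---|---|
| 0 | not estimable | 0.25 | no subjects | 0 |
| 1–4 | not estimable | 0.25 | 3 | 0 |
| 5 | 7 | 0.25 | 3 | 0 |
| 6–8 | 7 | 3 | 3 | 3 |
| 9–10 | 3 | 3 | 3 | 3 |

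**Combined vaccine group (n = 30), same clearance pattern.** Under reading A there is no median with 9 viremic, a median of 7 days with 15, 18 or 24, and 3 days with 30. Under reading B the median is 0.25 day with 9 or 15 viremic and 3 days with 18, 24 or 30.

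Every viremic subject behaves identically in all rows. Only the handling of the others changes.

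**The case against.** A reader might infer that the plan analyses never-viremic subjects, and all of placebo, as having the longest viremia, and so reverses the dose order. The documents do not support that. The SAP never classes a never-viremic subject as being without clearance, and reading B gives the same subjects the shortest time. Even under reading A, a censored subject is not assigned a long duration; the curve is held up or the median is lost. SAP 4.4.3 also asks for the numbers of events and censored observations beside the quantiles, so a placebo row would show 0 events and 6 censored. That all placebo samples will be negative is plausible but not stated.

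The impact is also limited. The same section reports proportions positive, geometric mean levels and geometric mean peaks by visit, specimen and dose, and SAP 4.4.4 adds the AUC. The interim analysis in SAP 3.12 uses RT-qPCR results but does not name Kaplan-Meier duration. The placebo repeat is conditional, and SAP 3.1 says the sample size was not chosen for formal hypothesis testing. In macaques every animal became viremic (protocol 1.1.3.2). If all vaccinees do too, the dose-group medians are unaffected under reading A. Those macaque doses (1.6×10^7 and 6.7×10^7 pfu) were above the trial's range, however, so they say little about the lower doses.

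These points lower the severity and rule out any claim about direction. They do not supply the missing definition, and neither reading yields a usable duration or placebo comparison.

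**Conclusion.** The concern holds as a failure of definition. SAP 4.4.3 leaves clearance undefined and applies its event and censoring rule to all ASaT subjects, so the median duration of viremia and the PHV01 versus placebo comparison are not interpretable on either reading.

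Under reading A, placebo has 0 events in 6, and a dose group of 10 has no estimable median with 4 or fewer viremic. With 10 of 10 viremic the median is unaffected; as the number falls, it rises and is then lost. Under reading B, never-viremic subjects, and vaccinees positive only after 6 hours, have an event at 0.25 day.

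The placebo results assume that all placebo samples are negative. The 3-day and 7-day medians are illustrative. The loss of the median at 4 or fewer viremic needs only follow-up to the last visit. The share viremic is unknown, so no size can be predicted for the actual trial. This is a should-fix: one secondary endpoint is affected, and the other viremia summaries stand.

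**What to change.** In SAP 4.4.3:

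1. Define a positive sample as a result at or above the LLOQ, as in protocol 3.1.3.
2. Define clearance as the first negative sample after the last positive one.
3. Run the Kaplan-Meier analysis descriptively by dose, in subjects with at least one positive sample, and censor only those still positive at their last sample.
4. Show the number and proportion ever positive in each group beside it, placebo included.
5. Delete the placebo Kaplan-Meier comparison.
6. Apply the same rule to the urine and saliva durations, for which 4.4.3 gives none.

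The downside should be stated in the SAP. Restricting to ever-positive subjects conditions on a post-randomisation outcome, so the medians describe viremic subjects and are not a comparison of randomised groups. If an all-subjects summary is wanted, set never-positive subjects to duration 0 and report it separately as a different quantity: in the illustration with 5 or fewer of 10 viremic its median is 0, against 3 days in the ever-positive.

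The cost is a few sentences of SAP text and one derivation. No new data are needed.

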3.1.2. Secondary Safety Endpoints

- PHV01 in blood on days 1 (at 0 and 6 hours), 2, 4, 8, 15, and 29, as detected by quantitative reverse transcription polymerase chain reaction (RT-qPCR)
 - o Proportion of subjects with viremia detected by RT-qPCR
 - o Median duration of viremia, determined by RT-qPCR
 - o Geometric mean level of viremia, geometric mean peak level of viremia, and area under the curve (AUC)
- PHV01 in urine, saliva, biopsy, joint fluid, vesicle fluid, or swab of other suspect lesions on days 1 (at 0 and 6 hours), 2, 4, 8, 15, and 29, as detected by RT-qPCR
 - o Proportion of subjects with PHV01 detected by RT-qPCR
 - o Median duration of PHV01, determined by RT-qPCR

o Geometric mean copy number of PHV01, geometric mean peak copy number of PHV01, and area under the curve (AUC)

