7.5.1. Analysis Addressing the Primary Study Objective (Safety)

Solicited symptoms occurring during the 28 days following vaccination will be summarized by treatment group and by relatedness. The incidence and severity of solicited AEs to the vaccine over the 28-day follow-up period will be calculated. Presentations will include the number and percentage of subjects with at least 1 local AE, and at least 1 general (systemic) AE, as well as the incidence of each AE individually.

The number of subjects with at least 1 incidence of an unsolicited AE reported up to 28 days after vaccination will also be summarized overall and by treatment group. The severity and temporal relationship of the unsolicited AEs to vaccination will also be assessed. Presentations will also summarize unsolicited AEs by grade and vaccine-relatedness. Serious AEs occurring at any point during the trial will be summarized and relatedness to vaccine will be assessed. The incidence rate of solicited AEs may be compared between each treatment group and placebo using Fisher's exact test and logistic regression.

The level of vaccinemia (on days 1 [at 0 and 6 hours], 2, 4, 8, 15, and 29) and shedding will be assessed on all subjects. The proportion of subjects with detected vaccinemia, as well as the geometric mean and AUC of vaccinemia level, will be presented at each time point where data are collected. The relationship between vaccinemia level and dose will be explored in a mixed model for repeated measures (MMRM) analysis that incorporates dose level, time, and other potential predictive factors. A similar model will be used to explore the relationship between dose and the AUC of the vaccinemia level.

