3. GENERAL STATISTICAL METHODS

3.1. Sample Size Justification

The sample size for this Phase 1 study (N=36 subjects; total N=10 per vaccine dose level [30 vaccinees and 6 placebo]) was selected to provide initial data and obtain estimates of safety and immunogenicity parameters and their respective variabilities. Group size is based on prior experience with ERVEBO safety studies and assumptions from the responses seen in the preclinical studies. This Phase I study is therefore designed with the goal of providing further information for better planning of future in-human studies. As this is a FIH study of PHV01, the sample size was established to provide reasonable information for descriptive purposes and not specifically designed for formal hypothesis testing.

Safety: With a sample size of 10 subjects, an upper bound of 30.9% is established for the 2-sided 95% confidence interval (CI) for the incidence of an AE in the case that the event is not observed according to the two-sided 95% (Clopper-Pearson) exact CI. Alternatively, when pooled together all 30 vaccinees, an upper bound of 11.6% is provided. This established the sample sizes needed to ensure minimal AE rates could be detected with confidence.

Immunogenicity: Clinical data for the rVSV-ZEBOV-GP Ebola vaccine showed that a dose of 3×10^6 pfu/mL yielded a Day 29 GMT IgG ELISA titer of 1400 EU/mL and geometric standard deviation (SD) of 3.3. Assuming that the variability in responses to PHV01 is similar, the proposed group sizes afford 80% (alternate 90%) power to detect a 6.4-fold (alternate 8.6-fold) increase, comparing geometric mean ELISA titer using a two-sided test with alpha=0.05 for each vaccine group with the placebo group. Alternatively, performing the same comparison against placebo by pooling all three treatment groups with a total 30 vaccinated subjects, we would have 4.7-fold and an alternate 5.9-fold with 80% and 90% power, respectively.

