3.3. Computing Environment

All descriptive statistical analyses will be performed using SAS statistical software Version 9.4, unless otherwise noted. Medical history and adverse events will be coded using the Medical Dictionary for Regulatory Activities (MedDRA) Version 26.1. Concomitant medications will be coded using the World Health Organization (WHO) Drug Dictionary Version Global B3 Sep 2023.

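### The combined-dose viremia-duration analysis depends on an undefined CI-overlap condition that is weak evidence of similar doses at 10 per group, and no direct comparison of duration between doses is planned

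*SAP*

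**What the plan says.** Duration is a named secondary safety endpoint in Protocol 3.1.2: "Median duration of viremia, determined by RT-qPCR". SAP 4.4.3 sets out its analysis. "The distribution for vaccine viremia duration by treatment group will be estimated by Kaplan-Meier methodology", with quartiles, event and censoring counts, and "appropriate 95% CIs will be presented". "Subjects without vaccine viremia clearance will be censored at the last evaluable assessment". The next sentence holds the condition: if the 95% CIs of "three PHV01 groups overlap then the analysis will be repeated comparing the combined PHV01 group with the placebo group".

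Group sizes are in SAP 3.1: "total N=10 per vaccine dose level [30 vaccinees and 6 placebo".

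Three other places bear on this:

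- SAP 3.5 plans a combined PHV01 group beside the dose levels with no condition attached. SAP 4.4.3 (proportion positive, level and peak) and SAP 4.4.4 (AUC) also summarise the combined group unconditionally. Only duration has a condition.
- Protocol 7.5.1 plans a dose model for other viremia measures: "The relationship between vaccinemia level and dose will be explored in a mixed model for repeated measures (MMRM) analysis", with a similar model for AUC. It does not cover duration. Protocol 7.5.2 adds only the median duration and a Kaplan-Meier graph.
- The introduction to Protocol 7 covers safety as well as immunogenicity endpoints and allows extra tests between dose levels. Neither document specifies one for duration.

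**The concern.** There are three linked problems.

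1. **The condition cannot be programmed as written.** Kaplan-Meier output will carry CIs for the 25th percentile, median and 75th percentile. The SAP does not say which is used, which CI transformation applies, whether all three pairs must overlap, or whether limits that meet at the same visit count.
2. **The condition depends on the data.** Whether a combined-versus-placebo result appears is settled by the observed intervals, although SAP 3.5 already pools the doses.
3. **Overlap says little about similarity.** There is no margin, and with 10 subjects per dose the intervals are wide. A real gradient can leave them overlapping.

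At stake is how a dose gradient in viremia duration is read, in a trial whose interim analysis is meant to guide Phase 2 dose selection (SAP 3.12). With no direct comparison planned, a reader has only the separate dose estimates and this condition to go on.

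**Working it through.** **The plan's own figures.** The documents give no power or overlap figure for duration. The nearest are the ELISA figures in SAP 3.1, and these reproduce. With SD = ln 3.3 = 1.19 and a two-sided noncentral t test, power at 6.4-fold and 8.6-fold (10 versus 6) is 79.9% and 90.0%. At 4.7-fold and 5.9-fold (30 versus 6) it is 80.4% and 89.8%.

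**Inputs.** From the documents: n = 10 per dose, and sampling at 6 hours and on Days 2, 4, 8, 15 and 29, which is 0.25, 1, 3, 7, 14 and 28 days after dosing. Assumed, because not given: log-normal duration, medians 1.5/3/6 days, geometric SD (GSD) 1.6, 2 or 3, every subject viremic, clearance dated to the next visit, and the condition applied to the median with all three intervals overlapping. SAP 3.3 says "All descriptive statistical analyses will be performed using SAS statistical software Version 9.4" but names no interval; treating log-log limits as the default is also an assumption.

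**What the interval is at n = 10.** Without censoring, Greenwood's sum is (1−S)/(nS). The log-log limits are exp(−exp(ln(−ln S) ± 1.96·se)), with se = √[(1−S)/(nS)] / |ln S|.

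- After the first clearance, S = 0.9: se = √0.0111/0.1054 = 1.00, lower limit 0.47, below 0.5. The interval starts at the 1st ordered time.
- After the eighth, S = 0.2: se = √0.4/1.609 = 0.393, upper limit 0.47, below 0.5. At S = 0.3 the upper limit is 0.58. The interval ends at the 8th ordered time.

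So the log-log interval is X1 to X8. The linear interval is X3 to X8, and the exact order-statistic interval is X2 to X9 (97.9% coverage).

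**Lowest versus highest dose, GSD 2.** Touching intervals overlap when X1 at 10^7 pfu is no later than X8 at 10^5 pfu.

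- Cleared by day 3: Φ(ln(3/1.5)/ln 2) = 0.841 at the low dose and Φ(ln(3/6)/ln 2) = 0.159 at the high dose. By day 7: 0.987 and 0.588.
- Low dose: P(X8 at day 3) = 0.796; P(X8 at day 7) = 0.203.
- High dose: P(X1 ≤ day 1) = 0.048; P(X1 ≤ day 3) = 1 − 0.841^10 = 0.822; P(X1 ≤ day 7) ≈ 1.
- Touching counted: 0.796 × 0.822 + 0.203 × 1 ≈ 0.86.
- Touching not counted: 0.796 × 0.048 + 0.203 × 0.822 ≈ 0.20.
- Linear limits, using P(X3 ≤ day 3) = 0.203 and P(X3 ≤ day 7) = 0.985: touching counted, 0.796 × 0.203 + 0.203 × 0.985 ≈ 0.36; not counted, 0.203 × 0.203 ≈ 0.04.

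**All three doses, by simulation (medians 1.5/3/6 days).**

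| GSD | Log-log, touching counted | Rank trend test power |
|---|---|---|
| 1.6 | about 52% | about 100% |
| 2 | 85% | 98% |
| 3 | 96-97% | 73-75% |

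At GSD 2 the condition passed and the trend test was significant in the same trial 83% of the time. On the same GSD 2 data, strict log-log overlap passes in about 18%, linear touching in 34-36% and linear strict in about 4%. With no dose effect, the log-log touching condition passes in over 99% and the trend test rejects in about 5%. The trend test here is the rank correlation of dose with clearance visit.

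**Further sensitivity.**

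- These figures end the interval at the last clearance visit when the curve falls to zero. Leaving the upper limit open there gives, at GSD 2, 86-89% (log-log, touching), 33-34% (log-log, strict) and about 48% (linear, touching).
- Medians of 2/3/4.5 days at GSD 2: the log-log touching condition passes in 98%, with trend power about 65%.
- Other duration models with the median doubling per step, log-log limits and touching counted: at planned visits, 91-99% for exponential, Weibull shape 1.5 or log-SD of at least 1.0. With exact times, about 20% at log-SD 0.5.

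**The case against.** The strongest reply is that little is lost. The SAP repeats the analysis rather than replacing it, so Kaplan-Meier quartiles, CIs and curves by dose are reported whether or not the condition is met. The pooled contrast is against placebo and cannot itself select a dose. This stands: no dose-level result is hidden.

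A reader might infer that the SAP takes overlap to mean equal duration, or that a real gradient almost always triggers pooling. The documents support neither. The SAP draws no conclusion about equality; that would be a guess at the condition's purpose. The pass rate is not a property of 10 per group: it is about half at GSD 1.6 even under the most permissive reading, and far lower under strict or linear readings.

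It is also fair that a gradient in persistence could show in proportions positive by visit, levels, peaks and AUC by dose, and in the protocol's exploratory dose models for level and AUC. Those bear on duration only indirectly, and the models are not carried into SAP 4.4.3 or 4.4.4.

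Finally, SAP 3.1 says the study was not sized for formal testing, and SAP 3.2 confines formal tests to immunogenicity endpoints. So a trend test must be labelled exploratory. It is not out of place, since Protocol 7 allows between-dose tests and covers safety endpoints. Precision will be limited: an approximate log-rank comparison of two doses with 20 events has 34% power for a hazard ratio of 0.5 and 87% for 0.25.

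**Conclusion.** The concern holds as an undefined, data-dependent trigger combined with a missing dose comparison. Under a four-fold difference in median duration between lowest and highest dose, the condition passes in anything from about 4% to 85% of trials at GSD 2, depending on conventions the SAP leaves open, and in 52-97% across GSD 1.6 to 3 under log-log limits with touching counted. That spread for identical data-generating assumptions shows that the rule is not specified. Where it passes often, it does so in data where an ordered test would usually detect the gradient.

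Every percentage rests on an assumed duration distribution, spread and set of medians. The case for removing the condition does not depend on any one of them: SAP 3.5 already provides for a combined group, so the condition serves no necessary purpose. This should be corrected, but it does not threaten the dose-level results.

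**What to change.** In SAP 4.4.3:

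1. Delete the overlap condition. Always present the combined PHV01 Kaplan-Meier summary and curve beside the three doses and placebo, as SAP 3.5 does elsewhere.
2. Add an ordered (trend) log-rank test of viremia duration across 10^5, 10^6 and 10^7 pfu, labelled exploratory and unadjusted for multiplicity.
3. State that overlapping CIs are not evidence of equal duration.
4. Name the CI transformation used for the Kaplan-Meier quartiles, so that the reported intervals are reproducible.

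The cost is a few sentences and one option in the existing Kaplan-Meier procedure, with no new data. The downside is one more unadjusted exploratory p-value.
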